2.3 Patient disposition, demographics and other baseline characteristics

2.3.1 Patient disposition

The number of patients screened, randomized, completed and discontinued from the study will be summarized for each study phase (i.e., screening, run-in, and treatment). In addition, the number of patients randomized, completed and discontinued from the 12-week treatment period will be summarized by country. Screened set and its subset of patients who received placebo study medication during the run-in period will be used for screening period and run-in period disposition tables, respectively. RAN will be used for treatment disposition outputs. Patients discontinued from the 12-week treatment period will also be summarized with reasons for discontinuation. Patients who discontinued study treatment but stayed in the study will be considered as completing the 12-week treatment period. Patients who discontinued study treatment but stay in the study are defined as patients with the date of study discontinuation or Visit 299 - the end date of study treatment > 0. Patient randomization numbers and whether they completed or discontinued from the study will be listed, with date of last dose and primary reason for discontinuation, including the unblinding date if applicable. Rescreening information will also be summarized mentioning the number of patients who were rescreened and how many of them were randomized.

Time to study discontinuation will be displayed graphically for each treatment group using a Kaplan-Meier curve for the FAS. The date of study discontinuation is defined as the maximum of the last known visit date for treatment period and the date of last dose of study medication. Patients who completed the study will be censored at the final study visit.

Number of patients with protocol deviations and protocol deviations that lead to exclusion from analysis sets will be tabulated by deviation category and treatment group for the RAN.

The number of patients included in each analysis set will be tabulated by treatment group for the RAN. Reasons for exclusions from analysis sets will be tabulated. Patient exclusion from analysis sets will be listed for all patients with reasons for exclusion (including protocol deviations).

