## 5.6 Study completion and discontinuation

### 5.6.1 Study completion and post-study treatment

Study completion for a patient will occur after he/she has completed 12 weeks of treatment (through to Visit 299) or has prematurely withdrawn. Completion of the study will be when

all randomized patients have completed 12 weeks of treatment and the post-treatment Follow-up visit.

Patients who have been screened when enrolment target has been met will be allowed to proceed onto study participation.

A Safety Study of QAW039 is planned. At sites participating in the Safety Study, patients who successfully complete 12 weeks of treatment in this study (Study A2316) may be offered participation in the Safety Study; patient participation in the Safety Study will be optional. Patients not entering the Safety study will complete the follow-up period and will not be given further access to study drug because the risk/benefit ratio will not yet have been substantiated and there are already other marketed therapeutic alternatives available to treat these patients. At the time of study completion or early termination, all patients will be placed on the appropriate asthma treatment as prescribed by the investigator.

The investigator must provide appropriate advice on the continued use of effective contraception for at least one week (at least 5 half-lives of QAW039) after the study completion visit (Visit 299) or premature study drug discontinuation and must follow up with the subject as appropriate at least to the end of this period.

The investigator must provide follow-up medical care for all patients who are prematurely withdrawn from the study, or must refer them for appropriate ongoing care.

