- If a patient develops a medical condition that requires consistent use of prohibited treatment as per [Section 5.5.8](#) or if patient exhibits a behavior of non-compliance regarding prohibited medication.

If discontinuation of study treatment occurs, the patient should NOT be considered withdrawn from the study. The patient should return to the clinic as soon as possible, after discontinuation of study drug, for a study treatment discontinuation visit. Treatment discontinuation visit assessments detailed in the "treatment discontinuation visit" (TD) in [Table 6-1](#) should be completed and recorded in the eCRF. The investigator must determine the primary reason for the patient's premature discontinuation of study treatment and record this information on the dosage administration record eCRF.

The investigator and study staff must discuss with the patient his/her continued participation in the study and request he/she continues attending study visits according to the study visit schedule with all assessments completed up to Visit 299. If the patient cannot or is unwilling to attend any further visit(s), the site staff should maintain regular phone contact with the patient, or with a person pre-designated by the patient. This phone contact should preferably be done according to the study visit schedule.

After study drug discontinuation, at a minimum, in abbreviated visits, the following data should to be collected at clinic visits or via telephone visits:

- new / concomitant treatments
- adverse events/Serious Adverse Events (SAE)

The investigator must also contact the IRT to register the patient's discontinuation from study drug.

If study drug discontinuation occurs because treatment code has been broken, please refer to [Section 5.5.9](#).

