Reversibility test (spirometry after administration of short-acting $\beta$ -agonist [SABA])	X**	X <math>\alpha</math>,<math>\beta</math>**									
¤To be performed prior to in-clinic witnessed study drug administration.
 
£To be performed after the second (-15 min.) pre-dose spirometry (may be performed after 10 AM <math>\pm</math> 1 h).
 
**If reversibility is NOT demonstrated at Visit 1, reversibility will be attempted at Visit 101. If not achieved, then one additional attempt allowed within 4 days following Visit 101.

Review Visit 1 or Visit 101 or the one additional attempt reversibility result from overread			S								
Asthma exacerbation monitoring	X	X	X	X	X	X	X	X	X	X	In case of an asthma exacerbation, the patient should be encouraged by the site to contact it for advice. If necessary, an unscheduled visit to the site may be arranged.
Serious adverse event monitoring	X	X	X	X	X	X	X	X	X	X	
Adverse event monitoring	X	X	X	X	X	X	X	X	X		
Liver event monitoring	X	X	X	X	X	X	X	X	X	X	If applicable, review lab results and clinical events as per Section 7.3 .
Renal event monitoring	X			X				X	X		If applicable, review lab results as per Section 7.4 .

Period	Screen	Placebo Run-in		Treatment						Follow-up	Notes
Visit Number (Site visits)	1	101	199	201	202	203	204	TD	299	301	Follow-up Visit 301 is only applicable for patients not participating in the safety study.
Treatment Week	-3	-1	0	0	2	4	8	TD	12	16	Visit 199 and Visit 201 occur on the same day.
Treatment Day	-21	-7	1	1	14	28	56		84	112	
Record deaths	X	X	X	X	X	X	X	X	X	X	
Contact IRT	S	S	S	S	S	S	S	S	S	S	
Randomize patient through IRT				S							
Assess and dispense rescue SABA to be used on an as-needed basis	S*	S	S	S	S	S	S	S	S**		*dispense SABA only **assess SABA only
Dispense study drug		S		S	S	S	S				Patients will be instructed to take study drug in the morning.
Assess compliance with study drug (count tablets in returned bottles)			S		S	S	S	S	S		
In-clinic witnessed study drug intake		X		X	X	X	X		X		Complete Dosage Administration Record (DAR)-Visit – at site visit.
Complete Study Drug Dosage Administration Record-Summary page			X		X	X	X	X	X		Complete DAR- Summary at each indicated visit to record compliance
Complete Study Disposition page (screening)	X										
Complete Study Disposition page (run-in)			X								
Complete Study Disposition page (end of treatment )									X		

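### SAP 2.3.1 counts a treatment discontinuer as completing the 12-week period if the study discontinuation date is only one day after the last dose

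*SAP*

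**What the plan says.** SAP 2.3.1 sets the status in two consecutive sentences. The first is "Patients who discontinued study treatment but stayed in the study will be considered as completing the 12-week treatment period". The second defines those who stayed as "patients with the date of study discontinuation or Visit 299 - the end date of study treatment > 0". The status feeds the counts of patients completing and discontinuing the period, including a table by country, and a further summary: "Patients discontinued from the 12-week treatment period will also be summarized with reasons for discontinuation".

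The next paragraph of the same section, written for the Kaplan-Meier plot, says that the "date of study discontinuation is defined as the maximum of the last known visit date for treatment period" and the date of last dose. This is the only definition of that date in the SAP.

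The protocol describes what happens after drug is stopped. Section 5.6.2 says: "The patient should return to the clinic as soon as possible, after discontinuation of study drug, for a study treatment discontinuation visit". In Table 6-1 the row "In-clinic witnessed study drug intake" has no entry in the TD column, and the end-of-treatment disposition page is scheduled at Visit 299, not at TD. Section 5.6.2 also provides for patients who will not come back: "If the patient cannot or is unwilling to attend any further visit(s), the site staff should maintain regular phone contact". Section 5.6.1 states: "Study completion for a patient will occur after he/she has completed 12 weeks of treatment (through to Visit 299) or has prematurely withdrawn".

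**The concern.** The evident intent is sensible: a patient who is off drug but followed to Week 12 has completed the period. The inequality does not implement that intent. A study discontinuation date marks the end of participation, yet the rule accepts it as proof that the patient stayed, provided it falls at least one day after the last dose. Since the protocol calls every treatment discontinuer back for a visit after stopping drug, and schedules no witnessed dose at that visit, a positive difference should be common among patients who leave early.

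What is at stake is the description of retention. The primary estimand in SAP Table 2-2 uses a treatment-policy strategy for discontinuation and relies on keeping patients in the trial after they stop drug. The disposition table is one place where a reader checks whether that succeeded. Under this rule it can show early leavers as completing and omit their reasons for leaving.

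**Working it through.** The plan states no expected completion figure, so there is none to reproduce. The check has two parts.

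**1. The rule applied literally.** Let L be the day of last dose, V the last treatment-period visit, and D the study discontinuation date. The flag is *completing* if D − L > 0, or if Visit 299 − L > 0. Using the SAP's only definition, D = max(V, L).

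| Treatment discontinuer | Calculation | Status under the rule |
|---|---|---|
| Last dose Day 30, TD visit Day 33, then leaves | max(33, 30) − 30 = 3 | completing |
| Last dose and last visit both Day 30, then leaves | max(30, 30) − 30 = 0 | discontinued |
| Last dose Day 20, TD visit Day 21, then leaves | max(21, 20) − 20 = 1 | completing |
| Last dose Day 40 at home, last visit Day 28, then lost | max(28, 40) − 40 = 0 | discontinued |
| Last dose Day 20, attends Visit 299 on Day 84 | 84 − 20 = 64 | completing (the intent) |

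The first two patients both leave 84 − 30 = 54 days before the planned Week 12 visit. They differ only in whether a visit fell after the last dose. Using the Kaplan-Meier date definition here is an inference, but the result does not depend on it: any study discontinuation date one day after the last dose gives a positive difference.

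**2. How many patients could be affected.** Inputs: 650 randomized patients (SAP Section 3), and 15% treatment discontinuation with half of these completing the trial (footnote to SAP Table 3-2).

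- Treatment discontinuers: 650 × 0.15 = 97.5.
- Of these, not completing the trial: 97.5 × 0.5 = 48.75, which is 48.75 / 650 = 7.5%.
- Period completion if early leavers are counted correctly: 100 − 7.5 = 92.5%.

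Let s be the share of early leavers with a visit after the last dose. The documents do not give s, so the values below are assumptions. Patients misreported = 48.75 × s; reported completion = 92.5 + 7.5 × s.

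| s | Misreported | Reported completion |
|---|---|---|
| 0 | 0 | 92.5% |
| 50% | 24 | 96.3% |
| 80% | 39 | 98.5% |
| 100% | 49 | 100% |

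Two qualifications apply to the ceiling.

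- The text of SAP Section 3 describes the retained half as having Week 12 FEV1 values, which is not the same as completing the trial. Some of the other half could be followed by telephone to Week 12, and these patients did stay. If a share t are (assumption), the ceiling is 48.75 × (1 − t): 36.6 patients (5.6 points) at t = 25% and 24.4 (3.8 points) at t = 50%.
- In the 20% discontinuation scenario of SAP Table 3-1, assuming the same half, the ceiling is 650 × 0.20 × 0.5 = 65 patients (10.0 points).

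**The case against.** The strongest reply is that the information is largely available elsewhere. SAP 2.4.1.1 reports treatment discontinuation with reasons, SAP 2.4.1.2 plots time to it, and a patient listing gives the date of last dose and the primary reason. The Kaplan-Meier plot of study discontinuation has its own date definition, and SAP 2.5.4 contrasts observed with imputed data graphically. The rule is the same in both arms, and the status is completion of a period, not 12 weeks of drug taken. All of this stands and limits the weight of the point. It does not remove it: no specified table separates patients off drug who reached Week 12 from patients off drug who left before it.

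A second reply is that the protocol works against early loss. Section 5.6.2 does not treat stopping drug as withdrawal from the study, and Section 5.6.4 does not allow a patient to be called lost to follow-up until the scheduled end-of-study visit has passed. This may keep the count low, but it does not change how the rule classifies a patient who does leave.

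Three stronger readings are tempting, and the documents do not support them.

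- **That attending Visit 299 is the only valid standard.** Section 5.6.2 makes telephone contact a recognized form of continued participation. Section 5.6.1 refers to weeks of treatment and also lets premature withdrawal count as study completion, so it does not set such a standard.
- **That the rank-based analysis and the Kaplan-Meier plot inherit the error.** The rank-based categories in SAP 2.5.5 are worded as completing or withdrawing from the trial, not the period. The SAP does not say that either analysis reuses this flag.
- **That the remapping in SAP 6.3 turns a late TD visit into attendance at Visit 299.** That section deals with using assessment data in place of a missed scheduled visit, not with disposition status.

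**Conclusion.** The point holds as an error in a stated rule. As written, SAP 2.3.1 can classify patients who left the study well before Week 12 as completing the 12-week treatment period and drop them from the reasons for discontinuing it. The overstatement lies between 0 and about 49 of 650 patients (0 to 7.5 points). The upper end is a ceiling, not an expected count. It assumes 15% treatment discontinuation, half of these completing the trial, every early leaver having a visit after the last dose, and none of them followed by telephone to Week 12.

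The consequence is confined to descriptive disposition tables. A reader might infer that the efficacy conclusion is at risk. It is not: the primary estimate, the power, the multiplicity procedure and the treatment-discontinuation summaries do not use this flag. The correction is worth making because it is cheap and the table bears on retention, but it is of modest importance.

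**What to change.** In SAP 2.3.1, replace the greater-than-zero rule. A treatment discontinuer counts as completing the period only if study participation continued to the scheduled Week 12 time point (Visit 299). State that a TD visit alone does not qualify. Report three separate rows:

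- off treatment, attended Visit 299;
- off treatment, followed by telephone only to Week 12 (in the study, without a Week 12 clinic assessment);
- off treatment, left the study before Week 12, with reasons.

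Leave the rank-based analysis and the Kaplan-Meier definitions unchanged.

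The cost is one derivation, a short change of SAP text and a few table rows. Table 6-1 already schedules the Visit 299 assessments and the end-of-treatment disposition page, and Section 5.6.2 already provides for telephone follow-up. The primary analysis is untouched. The downside is that the reported completion percentage may be slightly lower, by at most 7.5 points under the 15% planning assumption.

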2.3.2 Patient demographics and baseline characteristics

Demographics and baseline characteristics will be summarized by treatment group using the FAS set. Summaries will include age, gender, race, ethnicity, height, weight, BMI, pre- and post-bronchodilator FEV₁, percent predicted FEV₁, [REDACTED], FEV₁ reversibility, duration of asthma, number of asthma exacerbations in prior year, atopic asthma at entry into the study (Yes/No), smoking history (never/former), number of pack years, baseline ACQ-5, baseline AQLQ+12, [REDACTED], [REDACTED], and ICS use (alone, plus LABA, plus LTRA), ICS dose ranges (low, medium, high), [REDACTED] and daytime asthma symptom scores.

Background asthma therapy will be categorized into GINA steps and will be summarized at baseline. Background asthma therapy is defined as concomitant medication start date on or before Visit 1 and end date after Visit 1. Continuous variables will be summarized using

descriptive statistics (number of non-missing data, mean, standard deviation, median, first and third quartiles, minimum, and maximum) and categorical variables will be summarized in terms of the number and percentage of patients in each category including a category for missing data if any for the treatment group.

No statistical analyses will be provided for baseline comparability among the treatment groups.

In addition, the following categorizations of continuous variables will be done:

- Age: <18, 18 to <65, and ≥ 65 years;
- BMI: $\leq 30.0 \text{ kg/m}^2$ and $> 30.0 \text{ kg/m}^2$;
- Duration of asthma: < 1 year, 1 - 5 years, > 5 - 10 years, > 10 - 15 years, > 15 - 20 years, and > 20 years;
- Number of asthma exacerbations in prior year: 0, 1-2, 3, 4, ≥ 5
- pre-bronchodilator percent predicted FEV₁: $\leq 40\%$, $>40\% - \leq 50\%$, $>50\% - \leq 60\%$, $>60\% - \leq 70\%$, $>70\% - \leq 80\%$, $>80\%$
- ACQ-5: 1.5- < 2, 2 - < 2.5, ≥ 2.5 (< 1.5 will be added in case of protocol deviations)
- [REDACTED]

Derivation of the demographics and baseline characteristics

- BMI is calculated as: $\text{BMI (kg/m}^2\text{)} = \text{Weight (kg)} / [\text{Height (m)} * \text{Height (m)}]$
- Estimated number of pack years is calculated by the total years of smoking multiplied by cigarette packs smoked per day. This will be summarized as recorded on the eCRF. Smoking history in package years will be calculated as: (1 pack year = 20 cigarettes/day x 1 year or 10 cigarettes/day x 2 years).
- % of (pre-bronchodilator) predicted FEV₁ is obtained as a percentage of FEV₁ relative to the predicted normal value.
- FEV₁ reversibility is calculated as percentage increase of FEV₁ values after inhalation of bronchodilator relative to FEV₁ values prior to the inhalation. At visits with two pre-dose spirometry assessments, the FEV₁ from the 2nd pre-dose spirometry assessment (15 min prior to in-clinic witnessed study drug administration) should be considered the pre-bronchodilator FEV₁ value. A patient is considered to have demonstrated reversibility at clinic at baseline if there is an increase of 12% and ≥ 200 ml any particular visit prior to Day 1.
- Duration of asthma is calculated from the date of asthma first diagnosed recorded on the eCRF until the 1st visit. If the date is missing in day and/or month, it will be imputed as follows. If the year is before the first visit, the missing days will be imputed as the first of the month and the missing months will be imputed as July. If the year is the current year of the first visit, the missing days will be imputed as the first of the month and the missing months will be imputed as January.

- The total daily ICS dose at baseline will be categorized as low, medium, high based on the Appendix 6 in study protocol.

2.3.3 Medical history

Medical history will be coded with the Medical Dictionary for Regulatory Activities terminology (MedDRA) using the most recent version at the time of database lock. History/conditions as well as protocol solicited events for asthma will be summarized for the FAS set by primary system organ class and preferred term. Verbatim recorded history/conditions will be listed together with the coded terms, date of diagnosis/surgery and whether the problem was ongoing at start of the study.

2.4 Treatments (study treatment, rescue medication, concomitant therapies, compliance)

2.4.1 Study treatment / compliance

2.4.1.1 Duration of exposure

Duration of exposure to a treatment will be calculated as the number of days between the first dose date and the last dose date exposed to that treatment over the specified period (expressed as: Duration of exposure = Date of last known dose of study drug – Date of first dose of study drug + 1).

The duration of exposure will be summarized by treatment group for the safety set as a continuous variable with the standard descriptive statistics.

The number of patients who completed the 12-week study treatment and who discontinued prematurely will be shown including the reasons for discontinuation of study treatment. In addition, the duration of exposure will be summarized as a categorical variable classified into <4 weeks, >=4 to <12 weeks, >=12 weeks.

2.4.1.2 Compliance

Study drug compliance will be assessed. The overall compliance will be calculated as the percentage of days with study medication intake during the period from first intake to last intake taking into account the duration of the drug interruptions.

Percentage of days with study medication intake = $100 \times \text{number of days with study medication intake as per protocol} / (\text{Date of last known dose of study drug} - \text{Day 1} + 1)$.

Compliance will be categorized as <80%, 80% -100% and summarized by treatment group for the safety set.

Time to study treatment discontinuation will be displayed graphically for each treatment group using a Kaplan-Meier curve for the SAF. The date of study treatment discontinuation is defined as the date of last dose of study medication. Patients who completed the study treatment will be censored at the final visit for treatment period.

2.4.2 Prior, concomitant and post therapies

Medications started and stopped prior to study drug and taken concomitantly will be summarized by treatment group in separate tables in the SAF. The medication will be classified into “prior”, “concomitant” and “post” based on the start/end dates.

Prior: Any medication with a start date before Day 1.

Concomitant: Any medication with end date on or after Day 1 or ongoing at the end of trial or missing end date and start date on or before the end of the Treatment ~~+1 day~~.

Post: Any medication with start date after the end of treatment ~~+1 day~~, including medications taken in the Follow-up Period.

Medications can be considered both prior and concomitant.

Concomitant therapies will be recorded and summarized separately for asthma related medications / non-drug therapies and other medications. Concomitant asthma related medications will be summarized by pre-defined category. Concomitant medications not related to asthma will be summarized by pharmacological (ATC) class and preferred term. More than one ATC class per medication is possible and the medication will be reported under all applicable classes.

Short acting beta2 agonist (SABA) rescue medication usage (mean number of puffs) during the placebo run-in period will be summarized. Patients taking prohibited concomitant medications will be noted in the summary of protocol deviations.

All summaries will be by treatment group on the Safety Set.

